9. CLINICAL MONITORING

As this study is not a clinical trial, no clinical regulatory organisation will be involved in monitoring. We will comply to any monitoring requirements from the EDCTP.

10. STATISTICAL CONSIDERATIONS

10.1 STUDY OUTCOME MEASURES AND ANALYSIS

The main outcomes of interest are sensitivity and specificity of the point of care TransDot test during phase 3 of this study. Sensitivity will be calculated as the proportion of true positives (as determined by the composite gold standard of TB case definitions), who test positive on the TransDot test. Specificity will be calculated as the proportion of true negatives who test negative on the TransDot test.

For the primary analysis, the true positives as determined by the composite gold standard of TB case definitions, will consist of the Definite and Probable TB classes. The Possible TB class will be excluded as their diagnosis may involve a significant amount of uncertainty. This group will be included in a secondary analysis to show the TransDot test's performance in this uncertain group of participants.

Secondary outcomes of interest are positive and negative predictive values of the TransDot test, which will be calculated as the proportion of participants with positive or negative tests who are positive or negative according to case definitions, respectively.

Sensitivity, specificity, positive and negative predictive values will be reported with 95% confidence intervals.

Reproducibility of the test will be determined between laboratory based tests and point of care tests, as well as between the point of care tests conducted in the different countries, using the Kappa statistic for agreement.

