3 OBJECTIVES

Primary objective:

To prospectively evaluate the accuracy (sensitivity and specificity) of the UCP-LFA TransDot fingerprick test (hereafter called TransDot) in a laboratory-free manner, based on the six marker serum biosignature as a screening test for active TB, as compared to a composite gold standard (GeneXpert, MGIT culture, chest X-ray, TB symptom screen, response to antibiotics and response to TB treatment) in a population of TB suspects from resource-poor, high TB incidence settings in South Africa, Uganda, The Gambia, Namibia and Ethiopia.

Secondary objectives:

To evaluate the agreement between the TransDot test and laboratory based ELISAs first (both on serum), and subsequently between the TransDot (on fingerprick blood) and laboratory based TransDot (on serum).

To investigate the utility of a TransDot test at month 2 and month 6 as a marker of treatment response.

To identify additional host marker signatures that can be utilized for future improvement of diagnostic tests in the TransDot format or other point-of care tests that might become available in the future.

To collect appropriate additional host samples for future biomarker research.

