4. STUDY DESIGN

A non-interventional, diagnostic, prospective cohort design will be utilized, incorporating two separate sets of participants – overall a training set of 500 and a test set of 300 participants. The purpose of the training set will be to optimize the TransDot test and Reader to excellent sensitivity (90% or above) and acceptable specificity (80%). The test set will then be utilized to evaluate the TransDot test accuracy on fingerprick blood at the point-of-care site in a laboratory-free manner on a new prospective cohort of participants.

Training set participants will be recruited and receive investigations for TB. Blood samples will also be collected from them for performance of ELISAs and laboratory-based TransDot tests. These blood samples will be drawn at baseline, week 8 and week 24 at end of treatment for confirmed TB cases and at baseline and for non-TB cases.

Test set participants will be recruited and receive investigations for TB. A POC TransDot test will be performed on fingerprick blood at baseline, and at week 8 and week 24 in participants on TB treatment, as well as a laboratory based TransDot test on serum at baseline. The week 8 and week 24 TransDot tests will be used to investigate the test's utility as an indicator of treatment response.

Follow up of both sets of participants will be to week 24 for those found to have active TB, and week 8 for those found to be non-TB cases. There will be study visits at baseline, week 2 (GeneXpert negative participants only), week 8 and week 24 (participants on TB treatment only).

The TransDot test will be evaluated against a composite gold standard in the form of previously developed case definitions, consisting of GeneXpert, MTB culture, CXR, TB symptoms, response to antibiotics and TB treatment response. The case definitions will be applied to participant data by an outcome classification committee (see 4.2) who will remain blinded to the TransDot results of the test set, until after completion of all participants' outcome classification.

The primary outcome of interest will be performance of the TransDot test as compared to the gold standard, measured by sensitivity and specificity.

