For test set participants, serum will be collected for local laboratory based TransDot tests. POC TransDot tests will also be performed on fingerprick blood by the research nurse in a standardized manner across sites, at the baseline visit and before any results from the composite gold standard tests are available. A drop of blood will be applied to the test strip and the test strip will be submitted to the reader. The reported result will be recorded in the case report form. Agreement between the laboratory based and point of care TransDot tests will be calculated. Study investigators will be blinded to the TransDot test results until the final outcome classification has been completed for each participant. TransDot test results will also not be shared with clinic staff and no clinical decisions will be made based on TransDot test results.

A TransDot test will also be done at weeks 8 and 24 to investigate the utility of the test for monitoring treatment response as a secondary outcome. It will be compared to week 8 and 24 treatment outcomes as defined by sputum results, radiology, where applicable and TB symptoms.

It is expected that approximately one third of the participants will have a final diagnosis of active TB, whereas the non-TB cases will have a range of conditions including viral and bacterial lower respiratory tract infections and non-infectious conditions like chronic obstructive pulmonary disease.

The decision to treat for TB and the administration of treatment will remain the responsibility of the national healthcare system, although all relevant results to aid the decision will be shared with clinic staff. Referrals to the appropriate level of care for any accidental discoveries of other conditions or positive HIV results will also be done by the research team.

Participants at Stellenbosch University will receive R150 for participation in the study to compensate for travel expenses and loss of hours at work.

6.2 STUDY SCHEDULE:

Baseline visit (all participants)

Obtain written informed consent. Assign unique study participant ID. Conduct TB symptoms questionnaire. Obtain relevant medical history. Perform directed physical examination. Collect sputum samples for smear (except if results are obtainable from the government clinic), GeneXpert, MGIT culture and storage. Perform chest x-ray.

Perform pre- and post-test counselling for HIV test, except in participants who disclose their known positive status to study nurses.

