Collect 10ml blood for serum separation for laboratory based TransDot testing (Training and Test cohort).

Collect 4ml for Quantiferon (QFN) Gold test

Collect 16ml of blood for peripheral blood mononuclear cell (PBMC) isolation.

Collect 2.5ml of whole blood into PAXgene tubes for the study-specific biorepository.

Collect 2ml of saliva into the study-specific biorepository.

Collect 10ml urine into the study-specific biorepository.

Perform POC TransDot test and record the result (Test cohort).

Assure that all participants with symptoms of TB have attended the government clinic to obtain routine TB investigations.

Week 2 visit (only participants not diagnosed with TB by the baseline visit GeneXpert or sputum smear)

Conduct TB symptoms questionnaire and judge whether any symptoms improved or resolved on course of antibiotics for GeneXpert or smear negative patients.

Week 8 visit (all participants)

Conduct TB symptoms questionnaire.

Obtain relevant medical history.

Perform directed physical examination.

Perform CXR (only when indicated for treatment response).

Collect sputum samples for TB sputum smear (except if smear result is available from the government clinic), MGIT culture and storage (only participants on TB treatment or those for whom it is clinically indicated).

Collect 10 ml blood for serum separation for laboratory based TransDot testing (Training cohort).

Collect 16ml of blood for PBMC isolation (participants on TB treatment only).

Collect 10ml urine into the study-specific biorepository (participants on TB treatment only).

Perform POC TransDot test and record the result (Test cohort participants on TB treatment only).

Week 24 visit (only participants who started TB treatment)

Conduct TB symptoms questionnaire.

Obtain relevant medical history.

Perform directed physical examination.

Collect sputum samples for TB sputum smear (except if smear result is available from the government clinic), MGIT culture and storage.

Perform induced sputum if inadequate sputum volumes are available.

Perform CXR (only when indicated for treatment response).

Collect 10 ml blood for serum separation for laboratory based TransDot testing (Training and Test cohort). Collect 16ml of blood for PBMC isolation.

Collect 2.5ml PAXgene tube for study-specific biorepository.

Collect 2ml saliva for study-specific biorepository.

Collect 10ml urine into the study-specific biorepository.

Perform TransDot test and record the result (Test cohort).

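### Kappa, the only statistic named for fingerprick versus serum TransDot agreement, cannot show whether fingerprick gives more or fewer positives than serum

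*Combined protocol and SAP*

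**What the plan says.** Section 3 lists, among the secondary objectives, agreement between TransDot on fingerprick blood and laboratory TransDot on serum. The Protocol Summary says the same. Neither names a statistic.

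The pairs are planned. Section 4 gives each test-set participant a point-of-care fingerprick test at baseline, "as well as a laboratory based TransDot test on serum at baseline". The baseline visit in Section 6.2 collects serum for laboratory TransDot testing in both cohorts and schedules the point-of-care test in the test cohort.

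On analysis, Section 6.1 says only "Agreement between the laboratory based and point of care TransDot tests will be calculated". Section 10.1 says "Reproducibility of the test will be determined between laboratory based tests and point of care tests", and also between countries, "using the Kappa statistic for agreement". Nowhere do the documents plan discordant counts by direction, a paired difference in positivity, McNemar's test, or test-set sensitivity and specificity for the serum test.

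Two further points give context. The described optimisation, aimed at 90% sensitivity and 80% specificity, uses training-set serum (Sections 4 and 4.1). The evaluation uses fingerprick blood "on a new prospective cohort of participants".

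**The concern.** Kappa measures how far two classifications agree beyond chance and carries no sign. Two tests can disagree at random, or one can be consistently more often positive than the other, with the same kappa. Those findings mean different things for a screening test. Fewer fingerprick positives would tend to cost sensitivity, while more would tend to cost specificity.

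Because the described optimisation is on serum and the test is to be used on fingerprick blood, a systematic difference between the two ways of testing is what a reader of this secondary objective would want to see. Fingerprick sensitivity and specificity will be reported, but no serum figures from the same participants are planned beside them, and the training-set serum results come from other people. What is at stake is how informative one secondary analysis is.

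**Working it through.** **Inputs from the documents.** 300 test-set participants, about one third with TB, so 300/3 = 100 TB and 200 non-TB (Section 10.2). Target 90% sensitivity and 80% specificity (Section 4). Results are treated as positive or negative, as in Section 10.1. The plan gives no target, precision or expected value for kappa, so there is no stated figure to reproduce.

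**Assumed, not in the documents.** The number of discordant pairs and the size of any shift.

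**Step 1: the algebra.** Let a = both positive, b = serum positive and fingerprick negative, c = serum negative and fingerprick positive, d = both negative, n = a+b+c+d.

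- po = (a+d)/n
- pe = [(a+b)(a+c) + (c+d)(b+d)]/n²
- kappa = (po − pe)/(1 − pe)

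Swapping b and c leaves po unchanged and only reverses the order of the factors in pe, so kappa is identical.

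**Step 2: an example.** Take a = 105, d = 163 and b + c = 32, so po = 268/300 = 0.8933.

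| b v c | Serum positives | Fingerprick positives | pe | kappa | (c−b)/n, points | Exact McNemar p |
|---|---|---|---|---|---|---|
| 25 v 7 | 130 | 112 | 0.5169 | 0.779 | −6.0 | 0.002 |
| 16 v 16 | 121 | 121 | 0.5187 | 0.778 | 0.0 | 1.0 |
| 7 v 25 | 112 | 130 | 0.5169 | 0.779 | +6.0 | 0.002 |

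For the first row, pe = (130 × 112 + 170 × 188)/90,000 = 46,520/90,000 = 0.5169, and kappa = (0.8933 − 0.5169)/0.4831 = 0.779. The 95% half-width of the paired difference is 1.96 × √{[(b+c)/n − ((c−b)/n)²]/n} = 1.96 × √[(0.1067 − 0.0036)/300] = 3.6 points. The signed difference separates the three rows; kappa does not.

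**Step 3: what the added summaries could resolve.** This is an illustrative model only. Serum scores are normal with SD 1, with cut-off and TB mean set to give 90% and 80%. Fingerprick scores are shifted by ±0.25 SD, and the SD of the paired differences is 0.25, 0.5 or 1.0. The half-width formula is as above, applied within class (n = 100 or 200).

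| SD of differences | Shift | kappa | b v c | Sensitivity difference, points | Specificity difference, points |
|---|---|---|---|---|---|
| 0.25 | −0.25 | 0.86 | 19 v 2 | −5.1 ± 4.7 | +6.3 ± 3.6 |
| 0.25 | +0.25 | 0.85 | 2 v 21 | +3.7 ± 4.0 | −7.7 ± 4.0 |
| 0.5 | −0.25 | 0.78 | 25 v 7 | −5.1 ± 5.8 | +6.3 ± 4.6 |
| 0.5 | +0.25 | 0.77 | 8 v 27 | +3.7 ± 5.0 | −7.7 ± 5.0 |
| 1.0 | −0.25 | 0.60 | 38 v 20 | −5.1 ± 7.9 | +6.3 ± 6.2 |
| 1.0 | +0.25 | 0.58 | 22 v 41 | +3.7 ± 6.7 | −7.7 ± 7.0 |

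In the third row the TB class has b = 7.12 and c = 2.01 per 100. The difference is 2.01 − 7.12 = −5.1, with half-width 1.96 × √[(0.0913 − 0.0026)/100] = 5.8 points.

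At each SD, opposite shifts give nearly equal kappas and opposite effects on accuracy. Exact McNemar power in this model is about 99%, 87–90% and 60–64% for the three SDs. At a shift of 0.1 SD it is 36–38%, 20–21% and 13%.

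**The case against.** **Kappa answers the question asked.** The protocol speaks of agreement and reproducibility, and kappa measures that. Estimating a signed difference is not a stated aim. This stands, and it is why the point is a small improvement rather than an error.

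**The direction is in the data.** A reader might infer that the planned data could not show direction. They can: kappa cannot be computed without the 2x2 table, and its discordant cells carry the direction. Nothing in Section 6.1 or 10.1 forbids showing the table. The gap is only that the one planned summary leaves direction out, so whether it is reported is left to chance.

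**The comparison would not explain a missed target.** A reader might infer that paired results would reveal whether a shortfall from 90% and 80% arises because blood reads differently from serum or because the new cohort differs. The documents do not support that. Fingerprick tests are run by research nurses in the field. Serum tests are run in a laboratory after centrifugation, and stored aliquots are frozen (Sections 4.1, 6.1 and 6.3.2). The contrast mixes matrix, operator, setting and handling. Nor can it separate a cohort difference from training performance that was optimistic because the test was tuned on those participants.

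**Precision is limited.** In the model above, the sensitivity interval includes zero in five of six scenarios, although no specificity interval does. Class sizes of 100 and 200 are also a best case, since Possible TB is outside the primary analysis and some participants are classed as excluded. This stands.

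**Conclusion.** The point holds in a limited form. For a stated secondary objective, the only named statistic cannot show whether fingerprick testing is systematically more or less often positive than serum testing. That part is exact algebra and needs no assumption about the assay. The example of 32 discordant pairs and the shifts of ±0.25 SD are assumptions. They show what kappa would hide, not that a shift is likely. Adaptation to blood before phase 3 is neither described nor ruled out.

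A reader might also infer that optimising on serum biases the primary result. It does not: fingerprick sensitivity and specificity are estimated directly in the test set against the reference classification.

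This is a minor, nearly free improvement to one secondary analysis. Its yield is modest. In the illustrative model the paired sensitivity difference is known only to about ±4 to 8 points, so small shifts will often remain unresolved.

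**What to change.** Add to Section 10.1:

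> For test-set participants with both baseline results, the paired fingerprick-by-serum 2x2 table will be shown overall and by reference class. Beside kappa with its 95% CI, the discordant counts by direction (exact McNemar's test) and the paired differences in overall positivity, sensitivity and specificity with 95% CIs will be reported.

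Describe the result as point-of-care fingerprick versus laboratory serum testing, with matrix, operator, setting and handling taken together, and not as a pure matrix effect.

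The cost is a little more analysis and one more table. Both baseline tests are already planned, so no sample, visit or participant is added.

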However, a promising serum host inflammatory signature was identified during this project after investigation of more than 70 serum host inflammation markers, including acute phase proteins, T helper cell 1, T helper cell 2 and regulatory cytokines, soluble cytokine receptors and growth factors. The original set of markers for screening were chosen according to the availability of multiplexed assays (Luminex platform) and their known roles in inflammation and represented a wide spectrum of markers with diagnostic potential. The most promising host serum protein signature was subsequently validated on 687 people from five African countries with suspected TB, regardless of HIV infection status or ethnicity, providing the basis for the follow-up work suggested herein. The six-analyte signature of C-reactive protein (CRP), Interferon gamma (IFN-γ), pre-albumin, complement factor H (CFH), apolipoprotein A1 and inducible protein 10 (IP-10) ascertained TB disease with a sensitivity of 89% (CI 78 – 95%) and specificity of 76% (CI 68 – 83%), (positive predictive value of 61%; negative predictive value of 94%) ([7], [8]). Measurement of multiple markers and evaluation of their ratios offset a lack of disease specificity of individual markers. These performance characteristics would constitute a valuable screening test if converted into an inexpensive POC test and would prioritize individuals with a high likelihood of active TB for confirmatory testing by GeneXpert.

During the AE-TBC project, partner Leiden University Medical Centre (LUMC) developed and validated a user-friendly lateral flow assay (LFA) for simultaneous detection of multiple host TB biomarkers (cytokines and antibodies) in blood or other body fluids [9, 10]. These LFAs are likely to assist in rapid TB diagnosis in low-resource settings and were tested in the AE-TBC field sites. Importantly, our test formats utilize novel, nano-sized upconverting phosphor (UCP) reporter particles as read-out [11, 12, 13]. The UCP-technology delivers flexibility with respect to sensitivity and robustness as the ultrasensitive fluorescent label is not hampered by common auto-

fluorescence background. Moreover, the label does not fade, allowing UCP-test strips to be stored indefinitely for reanalysis. The LFA can also be modified for measurement of markers in fingerprick blood, which will further enhance its POC utility.

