4.1 STUDY PHASES

The study will be conducted in three phases. During the first phase a blood POC test using UCP-LFA TransDot [14] technology will be developed by LUMC, incorporating six serum markers, CRP, IFN- γ , pre-albumin, complement factor H, apolipoprotein A1 and IP-10. During this phase optimal antibody pairs for the lateral flow strips will be evaluated. In the event of a lack of optimal test performance for individual markers, replacement markers will be selected according to ongoing marker evaluation at the respective sites.

The TransDot test device technology will be optimized using serum from a subset of the first 500 recruited participants. These samples will be shipped to LUMC.

During a second phase of the study, TransDot devices will be available in the African laboratories, to test the remaining training set participants' serum locally. The first two phases will aim to optimise the sensitivity and specificity of the TransDot test.

The third phase will be the evaluation of the TransDot test in the field setting, by research nurses testing test set participants' fingerprick blood.

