5. STUDY POPULATION

5.1 SELECTION OF THE STUDY POPULATION

Adult participants with presumed active TB disease will be recruited in South Africa, the Gambia, Uganda, Namibia and Ethiopia. Each site will recruit approximately 160 participants with suspected TB, but faster recruiting sites may recruit more and slower recruiting sites fewer, until the desired overall total of about 800 participants is reached. In South Africa, up to 300 participants will be recruited from primary health care clinics in Cape Town.

Patients presenting to the health care facility with symptomatic pulmonary disease and a high likelihood of having tuberculosis will be enrolled and followed up for outcome classification.

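### The kappa planned between point-of-care TransDot tests in different countries has no paired readings, so it cannot be computed as written

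*Combined protocol and SAP*

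**What the plan says.** Section 10.1 names two uses of kappa in one sentence. The first is agreement between the laboratory-based and the point-of-care TransDot. The second is added with the words "as well as between the point of care tests conducted in the different countries, using the Kappa statistic for agreement".

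The rest of the document describes how point-of-care readings arise:

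- Section 4 states: "A POC TransDot test will be performed on fingerprick blood at baseline, and at week 8 and week 24 in participants on TB treatment".
- Section 4.1 describes phase 3 as a field evaluation "by research nurses testing test set participants' fingerprick blood".
- Section 6.1 says that the tests are "performed on fingerprick blood by the research nurse in a standardized manner across sites". One strip goes to the reader and the reported result is recorded. The only agreement calculation named there is laboratory versus point of care.
- Section 3 lists agreement of TransDot with ELISA on serum, and of fingerprick with laboratory serum TransDot. It lists no agreement between countries.

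On numbers by country, section 5.1 gives a target of about 160 per site but lets this vary ("faster recruiting sites may recruit more and slower recruiting sites fewer"), and adds: "In South Africa, up to 300 participants will be recruited from primary health care clinics in Cape Town". No allocation of the 300 test-set participants to countries is given.

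**The concern.** Kappa compares two or more ratings of the same unit, corrected for chance. A nurse in Kampala and a nurse in Banjul test different people, so there is no two-way table of one country's result against the other's. Standardised procedures across sites do not create such a table.

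Followed literally, the plan gives no between-country result. If someone forced a calculation by pairing unrelated participants, it would give a figure near 0 even for a test that performs identically everywhere. Since section 10.1 specifies no other between-country analysis, the question would then go unanswered or be answered by a method chosen after the data are seen. For a test intended for field use in five countries, consistency across them is worth an analysis that can be done.

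**Working it through.** The plan states no kappa value, number of pairs or precision for this analysis, so there is no figure to reproduce. The check is a count of pairs, followed by what the planned data could support instead.

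**1. Pairs available**

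Inputs: 300 test-set participants (sections 4 and 10.2); five countries (section 5.1); point-of-care testing at the participant's own visits (sections 4, 4.1, 6.1 and 6.2); residence in the study area for at least 3 months (section 5.2), which ties each participant to one site.

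- Country pairs: 5 × 4 / 2 = 10.
- Units with a point-of-care reading in both countries of a pair: 0 for each of the 10.
- Laboratory serum and fingerprick readings on the same participant at baseline: up to 300.

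**2. Other possible sources of pairing**

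- *Weeks 8 and 24:* these repeat the test in the same treated participant at the same site. They measure change on treatment.
- *Stored strips:* section 2.2 says that the label allows "strips to be stored indefinitely for reanalysis". This is a property of the technology; no section plans a re-read in another country.
- *Shipped specimens:* sections 6.3.2, 6.3.2.2 and 11.2 describe serum going to the Leiden laboratory. That is neither point-of-care testing nor a second field site.

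**3. What an arbitrary pairing would give**

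Assume 60 participants in each of two countries, one third with TB, sensitivity 90% and specificity 80% in both. The proportion testing positive is 0.9 × 1/3 + 0.2 × 2/3 = 43.3%. Pairing unrelated participants in 20,000 simulations gives a mean kappa of 0.00, with a central 95% range of −0.25 to 0.25.

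**4. What country-specific accuracy would give**

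The country split is an assumption, so two are shown, with the same prevalence and accuracy as in step 3. Intervals are exact (Clopper-Pearson) 95%.

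*Split A, equal:* 300 / 5 = 60 per country, so 20 TB and 40 non-TB.

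*Split B, South Africa at its ceiling share:* 300 / 800 = 37.5% of the test set. That is 112.5 participants there (37.5 TB, 75 non-TB) and 187.5 / 4 = 46.9 in each other country (15.6 TB, 31.3 non-TB). Rounded counts are used, so they add to 301.

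| Split | Country | Sensitivity | Specificity |
|---|---|---|---|
| A | each | 18/20: 68.3 to 98.8% | 32/40: 64.4 to 90.9% |
| B | South Africa | 34/38: 75.2 to 97.1% | 60/75: 69.2 to 88.4% |
| B | each other | 14/16: 61.7 to 98.4% | 25/31: 62.5 to 92.5% |

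Chance that at least one country has no false negatives at 90% sensitivity:

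- A: 1 − (1 − 0.9^20)^5 = 0.477.
- B: 1 − (1 − 0.9^38)(1 − 0.9^16)^4 = 0.567.

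Ordinary logistic regression with country terms would therefore break down about half the time.

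Power of an exact (Fisher-Freeman-Halton) test at 5%, with one country at 70% sensitivity and four at 90% (10,000 simulations): about 0.35 under A; under B, about 0.34 if the low country is a small one and 0.43 if it is South Africa.

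Participants classed as Possible TB are left out of the primary analysis and some others are classed Exclude, so the real counts would be smaller.

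**The case against.** The strongest reply is that the clause is loose drafting. The authors may have meant laboratory-versus-fingerprick kappa estimated in each country and then compared, which the data support. That may be so, but the sentence names the laboratory comparison first and then adds agreement between the point-of-care tests themselves. If the other meaning was intended, the sentence still needs changing.

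A second reply is that silence is not proof. The specimen procedures are cited but not reproduced, and the design schematic is not available, so a shared panel or strip re-reading might exist elsewhere. This justifies saying that no pairing is *described*. It does not go further, because the design, procedures, visit schedule, sample table, shipment and statistics sections are all present and contain no such step.

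Third, the consequences are limited. An analyst would see at once that there are no pairs, and nothing in the plan suggests pairing strangers. The simulation in step 3 illustrates a misuse; it is not a prediction. The intervals and power in step 4 likewise describe the replacement analysis under assumed splits and do not measure the defect.

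Fourth, country-specific accuracy is not reproducibility: it mixes test performance with patient mix, and a heterogeneity test here is weak. This stands. It is why the limits must be stated and why the heterogeneity test is the lesser part of the remedy.

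**Conclusion.** The concern holds. The between-country kappa in section 10.1 has zero paired units in the design as described and cannot be computed. This is an error in the stated analysis, beyond missing detail. The conclusion rests only on each participant being tested in one country and on no cross-country reading being described; it does not depend on the assumed country splits, prevalence or accuracy.

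The weight is moderate. The primary sensitivity and specificity, the sample size and the listed objectives are untouched, and the laboratory-versus-fingerprick kappa is valid. The sentence should be corrected before analysis.

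**What to change.** In section 10.1:

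1. Keep kappa for laboratory serum versus point-of-care fingerprick TransDot in the same participant, overall and by country.
2. Replace the between-country kappa with country-specific sensitivity and specificity, with exact 95% confidence intervals.
3. Optionally add a test of heterogeneity across countries, done separately in reference-positive and reference-negative participants, by an exact (Fisher-Freeman-Halton) or penalised (Firth) method.
4. State that differences between countries may reflect patient mix, such as HIV status, as well as the test; that per-country precision is low; and that a non-significant heterogeneity test does not show consistency.

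The cost is one revised sentence and a little more analysis, with no new data. The drawback is imprecise country estimates. If agreement between countries in the strict sense is wanted, a paired element such as a common panel or cross-site strip re-reading would have to be added and described. That would be extra work, and re-reading strips would assess the reader only, not the whole fingerprick procedure.
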